stress. Basal acyl-carnitines revealed accumulation of many long chain acyl-CoA's in type 2 diabetics including C18:0, C18:2-OH, and C20:4, which are thought to promote insulin resistance (Figure 11A). A significantly decreased GSH/GSSG ratio in type 2 diabetes individuals compared to lean volunteers suggest a more oxidized state, consistent with increased oxidative stress in insulin resistance (Figure 11B).

DAG and ceramide decrease mitochondrial

function. We administered 1,2-DAG, ceramide, dihydroceramide, and vehicle controls to isolated rat mitochondria in vitro to evaluate the impact on mitochondrial respiration using pyruvate and malate as substrates. DAG and ceramide decreased state 3 respiration, with no changes observed with dihydroceramide administration (Figure 12A and B). State 4 respiration did not change for 1,2-DAG and dihydroceramide, but increased significantly with increasing doses of ceramide. Both 1.2-DAG and ceramide decreased ADP/O ratios (Figure 13A and B), while dihydroceramide had no effect. These data indicate 1.2-DAG and ceramide reduced mitochondrial respiration and coupling, and are consistent with accumulation of mitochondrial lipids altering mitochondrial function.

Protocol Template CF-146, Effective 7/10/11

IV. Research Methods

A. Outcome Measure(s):

Primary outcomes:

Aim 1: Change in insulin sensitivity, change in sarcolemmal Di-C18:0 DAG and C18:0 ceramide, change in PKCepsilon and PP2A activity

Aim 2: Change in insulin sensitivity, change in mitochondrial/ER total DAG and ceramide content, change in state 3 mitochondrial respiration, change in GSH/GSSG, change in C18:0, C18:2-OH, and C20:4 acylcarnitines, change in GRP78

Aim 3: Change in mitochondrial state 3 and state 4 respiration in response to DAG and ceramide before and after lifestyle interventions

Secondary outcomes: Changes in other localized lipids and intracellular responses will be exploratory in nature. In addition, we will collect subjective and objective information about sleep and an exploratory analysis.

B. Description of Population to be Enrolled:

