Muscle biopsy specimens from specific aims 1 and 2 will be used for this aim. Fresh muscle biopsies samples will be permeabilized for mitochondrial respiration studies, as well as homogenized for mitochondrial respiratory chain complex activity. Measurements shown in Table 2A will be performed with and without the addition of increasing doses of specific 1,2- and 1,3-DAG and sphingolipid species, as shown in Table 2B, before and after each intervention. Ceramide and dihydroceramide will be administered as an equal mix of C18:0, C24:0, and C24:1 species, while 1,2- and 1,3-DAG will be an equal mix of Di-C18:0, C16:0/C18:0, and C16:0/C18:1 species. In addition to vehicle controls, we will also administer triolein to ensure responses observed are not due to a general effect of lipids on mitochondrial function.

Mitochondrial Respiration - All experimental measurements of oxygen consumption will be determined by a high-resolution respirometry Oxygraph-2K (OROBOROS Instruments, Innsbruck, Austria, see attached letter of support from [name]). Measurements will be performed at 37 °C and respiration rates expressed in nmolO2·min-1 ·mg·dry wt-1. Respiration will be normalized to vehicle control, since

Table 2A. Mitochondrial respiratory

substrate plan for permeabilized fibers	
Respiratory	Respiratory
substrates + ADP	substrates - ADP
 Glutamate + malate 	 Succinate +H₂O₂
 Octanoyl carnitine 	production
+ malate	
Succinate	

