basal respiration rates will vary based on training status and quality of muscle fibers from the biopsy. Permeabilization will be carried out directly in an oxygraph chamber with saponin (20 µg/mL) for 5 min before starting the measurements as previously described (49). To evaluate the in vivo condition, mitochondrial respiration in permeabilized muscle will be determined with glutamate + malate (GM), octanovl carnitine + malate(OM), and succinate as respiratory substrates (Table 2A). In the presence of either GM or OM, respiration is initiated with a saturating concentration of ADP (2 mM) and the Vmax of maximal ADP-stimulated respiration rate or state 3 respiration rate is determined. To evaluate the influence of DAG and sphingolipids on mitochondrial respiration, sphingolipids in isopropyl alcohol (1ul in 2ml respiration buffer), DAG in ethanol (1ul in 2ml respiration buffer), or vehicle controls are then added serially to measure affects of low, medium, and high lipid content. The intactness of mitochondrial membranes will then be validated by cytochrome c tests for each experiment. Only samples passing this quality test will be used further. Oligomycin is then given to measure mitochondrial proton leak. FCCP will then be titrated to uncouple the mitochondria and a maximal rate of the electron transport system rate determined. Antimycin A $(10 \ \mu M)$ is then added to determine the rate of residual oxygen consumption (Rox). Respiration rates are then corrected for Rox. Respiration kinetics of GM and OM will also be determined by adding ADP

Table 2B. Treatments for permeabilized fibers No treatment Vehicle control Lipid control -Triolein Low (1 ug/ml) Medium (2 ug/ml) High (4 ug/ml) Ceramide Low (1 ug/ml) Medium (2 ug/ml) High (3 ug/ml) 1,2-DAG Low (1 ug/ml) Medium (2 ug/ml) High (4 ug/ml) 1,3-DAG Low (1 ug/ml) Medium (2 ug/ml) High (4 ug/ml) Dihydroceramide Low (0.1 ug/ml) Medium (0.2ug/ml) High (0.3 ug/ml)

cumulatively and the maximum rates of respiration (Vmax) and values for apparent KmADP determined using Michelis-Menton kinetics.

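### Using each GM and OM run's own pre-addition state 3 rate, alongside the vehicle control, would sharpen the state 3 half of Aim 3's primary outcome at almost no cost

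*Combined protocol and SAP*

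**What the plan says.** Section IV.A gives Aim 3's primary outcome as "Change in mitochondrial state 3 and state 4 respiration in response to DAG and ceramide before and after lifestyle interventions". Section I adds the hypothesis that the DAG response will be weaker after endurance training.

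Section IV.C, Mitochondrial Respiration, names one scaling: "Respiration will be normalized to vehicle control, since", continued after a table with "basal respiration rates will vary based on training status and quality of muscle fibers from the biopsy". Rates are expressed per mg dry weight and corrected for residual oxygen consumption.

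The same paragraph sets out the order of a run. With GM or OM as substrate, ADP is added and "the Vmax of maximal ADP-stimulated respiration rate or state 3 respiration rate is determined". Sphingolipids in isopropyl alcohol, DAG in ethanol, "or vehicle controls are then added serially to measure affects of low, medium, and high lipid content". A cytochrome c check follows, and then "Oligomycin is then given to measure mitochondrial proton leak", before FCCP and antimycin A. Table 2B lists vehicle as a treatment in its own right: "Treatments for permeabilized fibers No treatment Vehicle control Lipid control -Triolein", followed by the four test lipids.

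No text says that the pre-addition state 3 rate is used in computing the response. Section IV.F covers Aim 1, Aim 2 and sleep, and contains no Aim 3 analysis that could supply the adjustment.

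**The concern.** The plan gives uneven fibre quality as its reason for normalising, but a vehicle run can remove only the part of that unevenness that all fibres of the biopsy share. If the response is the rate after lipid divided by the rate after vehicle, each rate carries the quality of its own fibre bundle. Bundle differences then enter twice at each visit and four times in the before-after change. The reading that would remove them is already taken: the state 3 rate of the same fibres just before the addition.

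Aim 3 looks for a change in a response, compared between arms, with 17 completers per arm (section IV.C). Error that could have been removed makes an attenuated DAG response harder to see.

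**Working it through.** **Is the vehicle reading from other fibres?** The protocol does not say so outright. Three features point that way: vehicle is an alternative to lipid in the sequence of additions, it is a separate entry in Table 2B, and each run ends with oligomycin, FCCP and antimycin A, after which the fibres cannot serve another treatment.

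**Inputs.** The documents state no power, effect size or variance for Aim 3, so there is no figure of the plan's to reproduce. All SDs below are assumptions on the log scale (roughly proportions):
- c: SD between bundles of one biopsy, 0.05 to 0.20
- d: error of one reading within a run, 0.05 to 0.10
- person-to-person SD of the pre/post change, 0.05

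**Model.** Log rate = biopsy level + bundle effect (SD c) + treatment effect + reading error (SD d).

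**Error variance of one state 3 response at one visit**
- Vehicle ratio only: 2(c² + d²).
- Own run first, then vehicle (double ratio): four readings, bundle effects cancel, 4d².
- Vehicle ratio adjusted for the pre-addition rates as covariate: 2(c² + d²)(1 − ρ²), with ρ = c²/(c² + d²).

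| c | d | vehicle only, SD | double ratio, SD | covariate, SD |
|---|---|---|---|---|
| 0.10 | 0.05 | √0.025 = 0.158 | √0.010 = 0.100 | 0.095 |
| 0.20 | 0.05 | √0.085 = 0.292 | √0.010 = 0.100 | 0.099 |
| 0.05 | 0.05 | √0.010 = 0.100 | √0.010 = 0.100 | 0.087 |
| 0.05 | 0.10 | √0.025 = 0.158 | √0.040 = 0.200 | 0.155 |

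The double ratio wins when c > d, ties at c = d and loses when c < d. The covariate form is not worse in any row. A simulation of 200,000 draws at c = 0.20, d = 0.05 gave SDs of 0.290 and 0.100 for the first two methods, with the same mean effect (−0.28) under both.

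**SD of the pre/post change** = √(2 × visit variance + 0.05²)
- c = 0.10, d = 0.05: √(0.050 + 0.0025) = 0.229, against √(0.020 + 0.0025) = 0.150.
- c = 0.20, d = 0.05: √(0.170 + 0.0025) = 0.415, against 0.150.
- c = d = 0.05: 0.150 under both.

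**State 4 and leak.** No pre-lipid leak rate is described, so the only same-run baseline is state 3. Let r be the correlation between a bundle's effects on leak and on state 3. Dividing leak by pre-addition state 3 in both runs gives variance 4c²(1 − r) + 4d².
- c = 0.10, d = 0.05, r = 0.5: √(0.020 + 0.010) = 0.173, against 0.158 for vehicle only.
- c = 0.20, d = 0.05, r = 0.5: √(0.080 + 0.010) = 0.300, against 0.292.
- r = 0: 0.224 against 0.158, and 0.412 against 0.292.

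For leak the ratio can therefore add noise.

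**The case against.** **The wording gives no formula.** Normalising to vehicle could mean expressing each run relative to its own start and then comparing with vehicle. This stands: the point is conditional on the plain-ratio reading. The own-run step is nowhere stated, though, and the proposed wording settles the matter either way.

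**Safeguards exist.** Rates are per mg dry weight, and only samples passing the cytochrome c test are used. These remove bundle size and damaged bundles. They do not remove graded differences in quality among bundles that pass.

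**The size is assumed.** This stands. With a person-to-person SD of 0.10 instead of 0.05, c = 0.10 and d = 0.05 give √0.06 = 0.245 against √0.03 = 0.173, a ratio of 1.4. Adding bundle-specific drift of 0.10 over the serial additions gives √0.10 = 0.316 against √0.07 = 0.265, a ratio of 1.2.

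**Stronger readings that the documents do not support.**
- A reader might infer that every run has a usable baseline. The pre-addition state 3 step is described for GM and OM only, and Table 2A also includes succinate without ADP.
- A reader might infer that one atypical vehicle bundle shifts every lipid at a visit, triolein included. Sphingolipids and DAG have different solvents and vehicle controls are plural, so a bad ethanol vehicle need not touch ceramide. Triolein's solvent is not stated. If triolein shared DAG's vehicle, that vehicle's error would cancel in the contrast between the two.
- A reader might infer that Aim 2's state 3 outcome rests on one bundle. Nothing in the documents says how many bundles it uses.

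**Conclusion.** The point holds as an inexpensive gain in precision for GM and OM state 3. The one scaling that the plan names leaves within-biopsy bundle differences in the response, although a same-run reading that would remove them is already taken. It does not show bias between randomised groups: the mean effect is the same under both scalings.

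Under the stated assumptions the SD of the pre/post change falls by about a third at c = 0.10, d = 0.05 (0.229 to 0.150) and by nearly two thirds at c = 0.20, d = 0.05 (0.415 to 0.150). It does not fall at c = d. The conclusion rests on the plain-ratio reading, on the inference that vehicle is a separate run, and, for the double ratio, on bundles varying more than repeat readings. It does not extend to dividing state 4 or leak by state 3.

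**What to change.** In section IV.C, for state 3 in the GM and OM runs, replace the normalisation sentence with one of these:

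1. Response = log(rate after lipid / same run's pre-addition state 3 rate) minus the same quantity for the solvent-matched vehicle run at the matching serial step.
2. Response = log(rate after lipid / rate after solvent-matched vehicle), adjusted for the two runs' pre-addition state 3 rates as a covariate. Entering the covariate as the log difference between the lipid run and its vehicle run cancels the level that training shifts in both.

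Option 2 is the safer choice if nothing is known about c and d. Existing laboratory data could show which is larger.

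Keep the vehicle runs, which remove solvent and time effects. For state 4 and leak, keep the vehicle comparison and use the pre-addition state 3 rate at most as a covariate.

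The cost is a sentence or two of wording, with no added tissue, run or visit. The downside is a small loss of precision for option 1 if c < d, or one extra model term for option 2.

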Obese men and women (BMI 30-40 kg/m²) will be recruited for this study who are between 30-50 years of age and sedentary (<2 hours/week of planned physical activity). Individuals with normal glucose tolerance (NGT), pre-diabetes, and newly diagnosed type 2 diabetes will be enrolled. Normal glucose tolerance is defined as a HbA1c of <5.7%, pre-diabetes as a HbA1c of 5.7-6.4%, and type 2 diabetes as a HbA1c of \geq 6.5% (31). Oral contraceptive use is allowed as long as women don't change their use, or lack thereof, during the course of the study. Exclusion criteria include: regular exercise more than 2 hours/week, medications that could affect glucose, lipid metabolism, thyroid disease, a history of lung disease, pregnancy, active cigarette smoking and severe plasma lipid disorders.

Inclusion criteria:

BMI: 30-40 kg/m²
Age: 30-50 years
Planned physical activity: <2 hrs/week
Glucose tolerance: NGT, pre-diabetes, and Type 2 diabetes
Normal glucose tolerance (NGT) is defined as HbA1c of <5.7%, pre-diabetes as HbA1c of 5.7-6.4%, and type 2 diabetes as HbA1c of ≥6.5% (31).
Oral contraceptive use: Yes or No as long as there is no change during the study
Medications: not taking TZD's, insulin
Thyroid status: TSH between 0.5-5.0 mU/L
Pregnancy status: Not pregnant
Nonsmoker (tobacco and any form of marijuana use)
Fasting TG <400mg/dl
FSH < 20 IU/L

C. Study Design and Research Methods

Ninety-two individuals (30-50 years old) will be screened to recruit sixty-nine obese men and women into the study. Individuals with and without prediabetes will be recruited to achieve a range of starting insulin sensitivities without confounding effects of medications used to treat type 2 diabetes. Volunteers will undergo an insulin clamp before and after block randomization by sex and pre-diabetes strata equally across intervention groups, into a three month

intervention consisting of: 1) endurance exercise training without weight loss, 2) diet-induced weight loss, or 3) delayed intervention control (Figure 5). The three month intervention will result in significant gains in fitness, weight loss, and improvements in insulin sensitivity, but is short enough to maximize retention.

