Exercise training and weight loss will differentially change DAG and sphingolipid content (11), revealing distinct changes in lipid localization, cellular signaling, metabolic function, and improvements in insulin sensitivity. We are expecting a 25% dropout rate, and are powered to complete testing on 17 individuals per group (51 total individuals). Subjects will be tested 48 hours after the last exercise bout to minimize acute exercise effects on insulin sensitivity. Women will be pre-menopausal and tested during the follicular phase (days 1-10) of the menstrual cycle to control for effects on insulin sensitivity.

Preliminary screening- Subjects will arrive after an overnight fast to the outpatient Clinical Translational Research Center (CTRC), and a fasting blood sample will be taken for a standard lipid panel, fasting glucose, TSH, and HbA1c. Women will take a pregnancy test. A physician will perform a history and physical, and subjects will fill out a dietary questionnaire, the NIH Dietary History Questionnaire II (DHQII), and the IPAQ physical activity questionnaire (33).

Strength and Exercise testing, body composition, maximal mitochondrial respiration, and MRI – Eligible subjects will undergo a Kin-Kom isokinetic dynamometer quadriceps strength test, Balke treadmill test to measure maximal work capacity (VO₂max) (34), a DEXA scan to determine body composition, a non-invasive test of maximal mitochondrial respiration, and MRI scan to measure leg muscle and fat mass, and liver fat content. During the maximal mitochondrial respiration test, volunteers will lie down on a table, and we will have a near infrared spectrometer measurement unit strapped to their leg. This unit uses a laser to measure the oxygen levels in the muscle. A blood pressure cuff will be wrapped around their upper thigh. To start the test, we will ask volunteers to make a muscle contraction for 20 seconds, after which we will intermittently inflate and deflate the blood pressure cuff every 5-10 seconds over a 5 minute period. This test will then be repeated. The total time for this test is 30 minutes.

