Muscle biopsy – Subcellular fractionation will be performed as described in Figure 1. Diacylglycerol (1,2- and 1,3- isomers), sphingolipids (dihydroceramide, ceramide, glucosylceramide, lactosylceramide, sphingosine, sphingosine-1-phosphate, sphingomyelin), triacylglycerol, phosphatidic acid, and long chain acyl-CoA species will be analyzed by [name] using the lipidomics platform in our laboratory. Subcellular fractions are fortified with internal standards (ISs), lipid extracted, and analyzed by an Agilent 1100 HPLC connected to an API 2000 triple quadrupole mass spectrometer (40). The 1,3- and 1,2- DAG isomers are separated chromatographically using a Hilic 2.1 micron, 3x100mm column. Concentration is determined by comparing ratios of unknowns to odd chain or deuterated internal standards. Incorporation of [U-¹³C]glucose into DAG glycerol, and [U-¹³C] palmitate into the sphingolipid backbone will be used to estimate *de novo* synthesis of DAG and sphingolipids (41; 42). Western blot analysis will quantify PKC translocation of θ , ε , β II, and δ isoforms in basal biopsies, as well as insulin signaling in basal and insulin stimulated biopsies including AKT^{ser473} /total, IRS-1^{Tyr612}/total, and AS160^{Thr642}/total using standard techniques (43). AKT^{Thr34} phosphorylation will be used to estimate PKC ζ activation by ceramide. PP2A activity will be measured using manufacturer instructions (Ser/Thr Phosphatase Assay Kit 1, Billerica, MA).

After the baseline clamp, subjects will be randomized into one of three interventions for three months:

1. Endurance exercise training - Participants will undergo supervised endurance exercise training administered by the Nutrition Obesity Research Center (NORC) Energy Balance Core (see attached letter of support from [name]) using well-established methods (44-48). Participants will perform supervised exercise 4x/week as well as exercise 1x/week on their own. Each 60 min session will include a short warm-up, 40 to 50 min of endurance exercise, and a cool-down. The exercise program will consist primarily of brisk walking or jogging, and will be supplemented with rowing, stepping, or elliptical exercise. The initial exercise prescription will be 30 minutes at 65% of maximal HR. During the first 2 weeks of training, exercise duration and intensity will be gradually increased

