to 45 min at 80 to 85% of maximal HR. This exercise training program resulted in a 9% increase in VO₂max in our pilot study (Figure 6A). Participants will be weighed weekly, and will be instructed to consume more food to prevent weight loss during this intervention. Maximal exercise testing will be performed half way through the intervention, and exercise prescriptions updated every 2 weeks.

2. Diet-Induced Weight loss - The weight loss program will be administered by the Clinical Core of the NORC (see attached letter of support from [name]). Participants will receive a low calorie diet consisting of 4-5 servings of vegetables per day and 4-5 meal replacements (Health Nutrition Technology Inc., Carmel California). No other food intake will be allowed. To reduce the risk of gallstone formation subjects will consume 2 teaspoons (10g) per day of vegetable oil. This diet will provide 890 kcal/d, 75 g of protein, 15 g fat and 110 g of carbohydrate and 100% of the DRI of all vitamins, minerals and micronutrients. This meal replacement program was used in our pilot study with an average 9% weight loss and 62% increase in insulin sensitivity in in 12 weeks (Figures 6B and 6C). Subjects will be weighed

weekly and will meet bi-weekly in group sessions to receive nutritional/behavioral counseling. After the 3month intervention, subjects will transition to their normal diet for 2 weeks of weight maintenance, supervised by research dieticians with extensive experience helping subjects maintain a weight-reduced state.

3. Delayed intervention control – This group of individuals will serve as our free-living control group, and ensure none of the changes observed in the diet-induced weight loss or exercise training interventions are due to receipt of health information, exercise testing, or contact with investigators. After finishing the study, they can choose to undergo the weight loss, exercise training, or combination intervention.

After finishing the intervention, participants will repeat the maximal exercise testing, MRI scan, DEXA measurement of body composition, sleep recording and the insulin clamp study after 2 weeks of weight stability on their typical diet.

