to exercise or weight loss only interventions. If we find minimal changes in insulin sensitivity with either intervention used in isolation, we will move to a combined intervention. Different degrees of success with the interventions are important to provide a spread in the data for changes in localized lipids and insulin sensitivity. An alternative approach would be to provide food for subjects to consume prior to both insulin clamps. We excluded this design because of the possibility of changing muscle lipid species and localization with changing dietary patterns. If individuals cannot maintain their weight within 2kg of starting weight in the exercise only intervention, they will be removed from the study. Our focus in this proposal is on DAG and sphingolipids, however, we will also measure changes in triglyceride, long chain acyl-CoA, and phosphatidic acid to determine other lipids related to changes in insulin sensitivity and/or cellular signaling. If there are no changes in PKC, we will evaluate changes in non-PKC DAG targets such as PKD and RasGRP1/4 to determine if these less studied DAG targets relate to insulin resistance.

Our typical muscle biopsy yield after removal of extra-muscular lipid, is approximately 160mg wet weight, and the tissue required for the assays in this project is 135mg wet weight, allowing all assays to be performed on the majority of biopsies. If muscle yield is limiting, we will prioritize analysis in the following order: subcellular fractionation (50mg) >western blot (15mg) >mitochondrial respiration (25mg) >PP2A activity (10mg) >PKC activity (35mg). We will also evaluate changes in other mitochondrial/ER lipids related to changes in mitochondrial function. In addition to those lipids listed under aim 1, we will also measure cardiolipin content as well as composition.

F. Data Analysis Plan:

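### Exercise-arm participants who drift more than 2 kg are removed after randomisation, in that arm only, with no follow-up or analysis planned for them

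*Combined protocol and SAP*

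**What the plan says.** The rule is in section IV.E (Potential Scientific Problems): "If individuals cannot maintain their weight within 2kg of starting weight in the exercise only intervention, they will be removed from the study". The wording is removal from the study, not only from training.

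The related text is in section IV.C:

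- **Timing.** "After the baseline clamp, subjects will be randomized into one of three interventions for three months". Allocation uses "block randomization by sex and pre-diabetes strata equally across intervention groups".
- **Arms.** They are "endurance exercise training without weight loss, 2) diet-induced weight loss, or 3) delayed intervention control".
- **Weight in the exercise arm.** "Participants will be weighed weekly, and will be instructed to consume more food to prevent weight loss during this intervention".
- **Control arm.** "This group of individuals will serve as our free-living control group". No limit on weight change is given for it.
- **Post-tests.** "After finishing the intervention, participants will repeat the maximal exercise testing", along with the imaging, sleep recording and clamp. No post-test is described for anyone who does not finish.
- **Numbers.** Sixty-nine are to be enrolled. "We are expecting a 25% dropout rate, and are powered to complete testing on 17 individuals per group (51 total individuals").

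Section IV.A makes change in insulin sensitivity a primary outcome for Aims 1 and 2. Section IV.F compares changes between groups by one-way ANOVA with Tukey pairwise tests, and takes the whole study group as n=51. It names no all-randomised set and no handling of removed participants. Neither section fixes when the 2 kg limit is judged.

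**The concern.** Randomisation makes the exercise and control arms comparable at baseline. A later exclusion that depends on how participants respond, and that operates in one arm only, can undo this.

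Weight is such a response. Training can lower it and the advice to eat more can raise it. The protocol itself treats weight loss as insulin-sensitising: section IV.C reports an average 9% weight loss and a 62% rise in insulin sensitivity in the pilot of the diet programme. Selecting exercisers on weight therefore means selecting on something linked to a primary outcome.

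The resulting contrast compares weight-stable exercisers with controls of any weight change. It estimates neither the effect of being assigned to exercise nor the effect of exercise at stable weight. The exercise-versus-diet contrast has the same asymmetry. Because no post-intervention clamp or biopsy is planned for those removed, the loss cannot be repaired at analysis. Baseline clamps and weekly weights would allow only a partial check.

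**Working it through.** **1. The plan's enrolment figure.** Inputs: 17 completers per group and 25% dropout (section IV.C).

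- Per arm: 17 / (1 - 0.25) = 22.7, rounded up to 23.
- Total: 3 x 23 = 69, which matches the plan.
- Expected completers per arm: 23 x 0.75 = 17.25, a margin of 0.25 of a person over 17.

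If removals came on top of dropout (rates assumed), the exercise arm would keep 17.25 x 0.9 = 15.5 at 10% removal, 17.25 x 0.8 = 13.8 at 20%, and 17.25 x 0.7 = 12.1 at 30%. If they fall within the 25%, there is no shortfall. The plan does not say which applies.

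**2. Illustrative bias.** None of these inputs is in the documents:

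- weight change W in the exercise arm is normal with mean m and standard deviation s;
- everyone outside ±2 kg is removed;
- W correlates r = -0.3 to -0.5 with change in insulin sensitivity, and the relation is linear.

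Let a = (-2 - m)/s and b = (2 - m)/s, with Φ and φ the standard normal distribution and density functions.

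- Fraction removed = 1 - [Φ(b) - Φ(a)].
- Shift in mean W among those kept, in SDs of W: k = [φ(a) - φ(b)] / [Φ(b) - Φ(a)].
- Bias in the exercise-arm mean, in SDs of insulin-sensitivity change = r x k. A negative value means the exercise effect is understated relative to all those randomised.

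Example: m = -0.5, s = 1.5 gives a = -1.00 and b = 1.67. Removed: 20.6%. Shift k = 0.180, so the retained mean is -0.5 + 1.5 x 0.180 = -0.23 kg. Bias is -0.3 x 0.180 = -0.054 to -0.5 x 0.180 = -0.090.

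| Mean (kg) | SD (kg) | Removed | Bias, r = -0.3 | Bias, r = -0.5 |
|---|---|---|---|---|
| 0 | 1 | 5% | 0 | 0 |
| 0 | 1.5 | 18% | 0 | 0 |
| 0 | 2 | 32% | 0 | 0 |
| -0.5 | 1 | 7% | -0.04 | -0.06 |
| -0.5 | 1.5 | 21% | -0.05 | -0.09 |
| -0.5 | 2 | 33% | -0.05 | -0.09 |
| -1 | 1 | 16% | -0.08 | -0.14 |
| -1 | 1.5 | 28% | -0.11 | -0.18 |
| -1 | 2 | 38% | -0.11 | -0.18 |
| +0.5 | 1 | 7% | +0.04 | +0.06 |
| +0.5 | 1.5 | 21% | +0.05 | +0.09 |
| +0.5 | 2 | 33% | +0.05 | +0.09 |

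A larger assumed loss, mean -1.5 kg with SD 1.5 to 2, removes 38-44% and takes the bias to about 0.28 SD at the stronger correlation.

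**3. Scale.** The standard error of a two-group difference at 17 per group is √(2/17) = 0.34 SD. A bias of 0.18 SD is about half of that (0.18 / 0.34 = 0.53).

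**The case against.** The strongest reply is that the rule enforces the arm's definition. The design wants exercise without weight loss so that its mechanism can be separated from that of the diet arm, and an exerciser who loses weight blurs this. The protocol never says it targets the effect of assignment. The purpose is legitimate, but filtering one arm does not achieve it: the weight-stable effect needs a comparator restricted or adjusted in the same way.

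Several further points limit the weight of the concern:

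- Every bias input is assumed. Symmetric drift gives zero, and the main range stays near half a standard error or below. This stands.
- The text removes those who cannot hold their weight, in an arm weighed weekly and told to eat more. Removal may follow only failed correction, so the modelled rates could be too high. This stands.
- Someone removed does not complete testing, so counting removals within the 25% is a natural reading. It is plausible, but it is not written.
- The missing analysis set affects dropouts in every arm. True, but the 2 kg rule adds a loss that the protocol itself imposes on one arm.
- Post-testing follows two weeks of weight stability with no arm named. That condition does not cap change from baseline in controls.
- Retesting is burdensome: an overnight stay, isotope infusions, a clamp and two biopsies. This is a real cost, although these are tests already planned for each enrolled participant.

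**Conclusion.** The concern holds. Followed as written, the plan excludes participants after randomisation, in the exercise arm only, on a variable that the intervention can change and that the protocol links to a primary outcome. The existence of the rule and its asymmetry are clear from the text.

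Its effect on the result is uncertain. Because the limit works in both directions, the sign of the bias is not fixed: removing those who lose weight tends to understate the all-randomised exercise effect, and removing those who gain tends to overstate it. Under the main assumptions the range runs from 0.18 SD understated, through zero, to 0.09 SD overstated. That is modest beside the sampling error of this trial. No loss of power is claimed, because the removal rate is unknown and removals may already be counted in the 25%.

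This should be fixed, and before removals occur, because the missing clamps and biopsies cannot be obtained later.

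**What to change.** Amend sections IV.E and IV.F as follows.

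1. Separate leaving the intervention from leaving the study. Participants outside the 2 kg limit are still invited to the planned post-intervention tests and are analysed in their randomised arm in the ANOVA and Tukey comparisons. Whether and when they stop training remains for the investigators.
2. Add a supportive weight-stable analysis of exercise versus control that applies the same 2 kg restriction to both arms or adjusts for weight change. Define the flag in both arms as post-test weight minus baseline weight.
3. Report the number outside the limit by arm and direction, and state whether any removals count within the 25% dropout.

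The cost is protocol and analysis-plan wording, plus post-tests for those who would otherwise be lost. At the 7-38% removed when mean weight drifts, that is about 2 to 9 of the 23 in the arm (23 x 0.07 = 1.6; 23 x 0.38 = 8.7).

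There are two downsides. The as-randomised exercise estimate may carry a small weight-change component. The weight-stable analysis still conditions on a post-randomisation variable, so it can only be supportive.
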